7.8 Withdrawal criteria

If a client experiences a severe relapse in their mental health and is unable to continue with the trial they will be withdrawn.

If a client develops new symptoms of severe mental illness outside the remit of F32-33 (depression), F40-41 (anxiety) or F53 (Mental and Behavioural disorders associated with the puerperium, including postnatal depression). This can include (but is not exclusive to) Psychosis, Mania, Substance Misuse or Physical Self Harm.

If a client experiences difficulties in their physical or pregnancy health that mean they are unable to participate in the trial they will be withdrawn.

If a participant's baby or child becomes unwell requiring ongoing medical support this will take priority and the client will withdraw from the trial.

If a participant places another participant (or their child / family) at risk they will be withdrawn from the trial. This can include (but is not exclusive to) physical harm, mental distress, safeguarding concerns.

Clients are free to withdraw from the research at any point if they feel it is not benefiting their mental health. Withdrawing from the research will not affect ongoing care or future referrals to other treatments or therapies in any way.

If there is a dropout rate of greater than 75% of the CBGT group the trial will be ceased.

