The evidence base for using Cognitive Behavioural Group Therapy when treating perinatal depression and anxiety is modest. A 2010 systematic review (Stevenson et al., 2010) assessing CBGT for postnatal depression found only six studies met the inclusion criteria for quantitative review. The authors highlighted a lack of Random Control Trial evidence of CBGT as treatment for postnatal depression as a limitation. This review found three studies indicated group psychoeducation incorporating CBT as effective, however the inconsistent and low quality nature of these studies limited proposing CBGT as a service provision.

For treatment of perinatal anxiety a 2016 study compared CBGT with interactive lectures for reducing anxiety during pregnancy (Salehi, Pourasghar, Khalilian and Shahhosseini, 2016). CBGT was found to be more effective in reducing anxiety than interactive lectures, but the difference was not significant. Regarding anxiety in childbirth a 2020 paper demonstrated GCBT useful for pregnant women with tokophobia (Ghavami, Ghanbari Hashem Abad, Saffarian and Khakpour, 2020).

The evidence base for CBGT via Video Communication in the Perinatal period is very small. However a 2017 quantitative survey of pregnant women found the majority would consider some form of computer-based therapy for mental health treatment during pregnancy (Hantsoo et al., 2017). Video telehealth therapy (patient engaging with a therapist via a web camera) was the most common considered. Computer assisted Cognitive Behavioural Therapy has been found to show a response for pregnant women (Kim et al., 2014) but this is based on computer software rather than a group video communication approach.

The treatment intervention for this research study is Cognitive Behavioural Group Therapy (CBGT). Group sessions will follow an adaptation of models outlined in:

Söchting, I., 2014. Cognitive Behavioral Group Therapy: Challenges And Opportunities

Wenzel, A. and Kleiman, K., 2015. Cognitive Behavioral Therapy For Perinatal Distress.

Additional utilisation of relevant journal articles and texts will also be adapted and referenced as required.

This research is a Case Series and there are no controls nor comparator groups.

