3.3 Outcome measures/endpoints

3.3.1 Primary endpoint/outcome

Primary Outcome

The primary outcome are changes in outcome measure scales over the course of the CBGT group. The aim would be a reduction in scores of the EPDS, GAD-7, CORE-10 and CORE-OM for each participant.

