3.3.4 Table of endpoints/outcomes

Objectives	Outcome Measures	Timepoint(s) of evaluation of this outcome measure (if applicable)
Primary Objective To monitor the change in outcome measure scales over	Edinburgh Postnatal Depression Scale, GAD-7 anxiety scale and CORE-10 scale	The scales will be scored at each CBGT session and the follow up session.
the course of the Cognitive Behavioural Group Therapy.	CORE-OM scale	The CORE-OM scale will be scored at the first and final session.
Secondary Objectives To allow participants to give basic feedback on the group	A Likert scale (with free text availability) asking five questions.	Completed at the follow up session

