7.4 Research Intervention

When ten clients (minimum six) complete this process a convenient time and start date will be arranged to commence the therapy sessions. Each therapy session will have a duration of two hours and take place at approximately at the same time each week for ten weeks. There will be a follow up session at eight weeks.

Each session will be led by two professionals with experience of CBT therapy. The Chief Investigator (an experienced consultant perinatal psychiatrist with a postgraduate qualification in CBT) and a higher trainee psychiatrist (this signifies a trainee who has completed a minimum of 3 years core psychiatry

training involving 'short' and 'long' cases in psychotherapy and achieved successful membership of the Royal College of Psychiatrists requiring examination in various therapeutic techniques including CBT).

The treatment intervention for this research study is Cognitive Behavioural Group Therapy (CBGT). Group sessions will follow an adaptation of models outlined in:

Söchting, I., 2014. Cognitive Behavioral Group Therapy: Challenges And Opportunities

Wenzel, A. and Kleiman, K., 2015. Cognitive Behavioral Therapy For Perinatal Distress.

Additional utilisation of relevant journal articles and texts will also be adapted and referenced as required.

The group is a transdiagnostic group, meaning it includes different diagnoses: depression, anxiety syndromes and postnatal depression. Therefore reference will be made to McEvoy and Nathan, 2007 Effectiveness of cognitive behavior therapy for diagnostically heterogeneous groups: A benchmarking study and Hamilton et al., 2012 Exploring the Effectiveness of a Mixed-Diagnosis Group Cognitive Behavioral Therapy Intervention Across Diverse Populations.

Each session will use CBT techniques. A complete Session outline is available in the Interview Schedule.

The follow up session will review progress or setbacks made to that point, give encouragement and reinforce therapeutic techniques used. It will also aim to troubleshoot any problems with CBT techniques learnt.

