7.5 Research intervention Outcome Measures

Prior to each session clients will complete the following outcome measures.

- The Edinburgh Postnatal Depression Scale (Cox, Holden and Sagovsky, 1987),
- GAD-7 anxiety scale (Spitzer, Kroenke, Williams and Löwe, 2006)
- Core 10 short measure (Barkham et al., 2013).

These scales will be sent by either email or physical post to the clients to allow them to complete them.

A CORE-OM will be completed prior to the first session and following the final session, again sent by email or physical post. Data from these will be collated for the purpose of the research.

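### Section 7.8 withdraws women from the trial partly on outcome-related grounds, and no scores are planned after withdrawal, so a completer-based change risks overstating improvement

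*Protocol*

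**What the plan says.** Protocol section 7.8 sets the withdrawal rules. The first reads: "If a client experiences a severe relapse in their mental health and is unable to continue with the trial they will be withdrawn". The section also names new symptoms of severe mental illness outside the eligible diagnoses (self-harm is among the examples) and confirms that women may leave the research if they feel it is not helping. Its other grounds are physical or pregnancy health, a sick child, and risk to other participants. The trial stops only if dropout exceeds 75%.

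Section 3.3.1 defines the outcome: "The primary outcome are changes in outcome measure scales over the course of the CBGT group". It adds: "The aim would be a reduction in scores of the EPDS, GAD-7, CORE-10 and CORE-OM for each participant".

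On timing, section 7.5 says "Prior to each session clients will complete the following outcome measures", and the table in 3.3.4 says of EPDS, GAD-7 and CORE-10: "The scales will be scored at each CBGT session and the follow up session". CORE-OM is taken only at the start and end of the ten-session course. On delivery, 7.5 says: "These scales will be sent by either email or physical post to the clients to allow them to complete them".

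Section 11.3 promises follow-up and care under medical supervision when an adverse event ends a woman's treatment. It does not mention the outcome scales.

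On size and design, section 7.4 says "When ten clients (minimum six) complete this process a convenient time and start date will be arranged to commence the therapy sessions", and section 2 says "This research is a Case Series and there are no controls nor comparator groups".

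**The concern.** Section 7.8 treats leaving the therapy group and leaving the trial as one event, and some of its triggers are close to what the scales measure. A woman with a severe relapse who cannot continue would be expected to show a poor change on EPDS, GAD-7 or CORE-10. Under the plan as written, no score of hers is scheduled after that point.

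If the results are then summarised as the change among women with end-of-course scores, the worst courses are under-represented and the mean shifts towards improvement. A control arm subject to the same loss might offset part of this, but there is none. One woman is 10% of a group of ten and about 17% of a group of six, so one or two such losses can move the summary visibly. The study's stated aim is to explore efficacy, so the direction of this shift matters.

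**Working it through.** **The plan's own figure.** There is none to reproduce. The protocol gives the sample size (ten, minimum six) without a calculation, and states no SD, effect size or expected dropout. Everything below except step 1 is an illustration under stated assumptions.

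**1. How much loss the plan tolerates.** The stopping limit is dropout above 75%.
- Of ten: 7/10 = 70%, so the trial continues with 3 women; 8/10 = 80% stops it.
- Of six: 4/6 = 67%, so it continues with 2 women; 5/6 = 83% stops it.

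**2. Completer mean when the worst k of n are lost.** Assume a true mean change of 0, normal changes with SD 1 (positive = worse), and that exactly the k women who worsen most have no final score. The total of all n changes has expectation 0, so

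expected completer mean = −(sum of the k largest expected order statistics) / (n − k).

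The three largest of ten standard normal values have expectations 1.539, 1.001 and 0.656; the two largest of six have 1.267 and 0.642.

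| n | k | Sum | Divided by n − k | Apparent change |
|---|---|---|---|---|
| 10 | 1 | 1.539 | 9 | −0.17 SD |
| 10 | 2 | 2.540 | 8 | −0.32 SD |
| 10 | 3 | 3.196 | 7 | −0.46 SD |
| 6 | 1 | 1.267 | 5 | −0.25 SD |
| 6 | 2 | 1.909 | 4 | −0.48 SD |

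A simulation with 400,000 replicates gives the same values. In points, for a scale with an assumed SD of change of 5 (range 4 to 6), losing the worst 2 of 10 gives 0.32 × 5 = 1.6 points (0.32 × 4 = 1.3 to 0.32 × 6 = 1.9).

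**3. If only severe worsening leads to withdrawal.** Suppose a woman leaves only when she worsens by more than c SD. The mean among those who stay is −φ(c)/Φ(c), and the share of them who have still worsened is (Φ(c) − 0.5)/Φ(c).
- c = 1: 0.242/0.841 = 0.29 SD apparent improvement; 15.9% leave; 0.341/0.841 = 41% of those who stay have worsened.
- c = 2: 0.054/0.977 = 0.06 SD; 2.3% leave; 0.477/0.977 = 49% of those who stay have worsened.

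**4. If the last weekly scores of withdrawn women are used.** Suppose those scores capture half of the worsening. The mean over all n women is then −0.5 × (sum in step 2)/n. For n = 10 and k = 1 to 3 this is 0.5 × 1.539/10 = 0.08 SD to 0.5 × 3.196/10 = 0.16 SD. For n = 6 and k = 1 to 2 it is 0.5 × 1.267/6 = 0.11 SD to 0.5 × 1.909/6 = 0.16 SD.

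This rescue is not available for CORE-OM. A woman withdrawn before the end of the course has one CORE-OM score and no change.

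**5. If every woman supplies end-of-course scores.** The expected mean returns to the true value, 0 in this illustration.

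**The case against.** The strongest case on the other side has four parts.

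- **The rule is narrow.** A reader might infer that anyone who deteriorates is removed, so that the results rest on women who did not worsen. The text does not support this. It requires a severe relapse together with inability to continue. Women who worsen less stay in and are scored; in step 3, 41% to 49% of those who stay have worsened. Several other grounds (physical health, a sick child, risk to others) are not defined by the outcome, and leaving for lack of benefit is the woman's own choice.
- **Nothing forbids later scores.** A reader might also infer that the protocol stops outcome collection at withdrawal. It does not say so. The gap follows from a session-based schedule and from silence. Because the scales go by email or post, completing them does not require attendance.
- **Earlier scores exist.** EPDS, GAD-7 and CORE-10 are repeated at each session, and the aim is framed for each participant. Scores before withdrawal may show the worsening. This stands, with one limit: they are completed before a session, so the last one may precede the relapse.
- **No completer mean is planned.** The analysis set and the handling of missing scores may be in a statistical analysis plan that is not shown, and their absence from the protocol is not a fault.

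What remains is a matter of data collection and consent, which belongs in the protocol. No analysis plan can recover scores that were never requested.

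**Conclusion.** The point holds as a risk arising from how section 7.8 and the schedule fit together. Withdrawal is from the trial and not only from the group, some of its grounds are related to the outcome, and no scores are planned afterwards. Missing late scores will therefore depend partly on outcome, and nothing in an uncontrolled series of six to ten women offsets that.

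A reader might go further and conclude that the study will overstate benefit. The documents do not establish this, because it depends on a completer-based summary that the protocol does not specify. Under such a summary, with a true mean change of 0 and exactly the worst 1 to 3 of 10 lost, the apparent improvement is 0.17 to 0.46 SD. It falls to 0.06 to 0.29 SD if only worsening beyond 1 to 2 SD leads to withdrawal, and to 0.08 to 0.16 SD (1 to 3 of 10 lost) if last weekly scores capture half the worsening. The SD, thresholds and number lost are all assumptions. CORE-OM, with only two time points, is the most exposed scale.

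**What to change.** In section 7.8, distinguish two events: a woman stops attending the group, and a woman withdraws from the research or from data collection. State that women who stop the group will, with their consent and unless their care team advises against contact, still be sent the scales by the existing email or post route:

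- at the end of the ten weeks: EPDS, GAD-7, CORE-10 and CORE-OM;
- at the eight-week follow-up: the scales scheduled then. The table in 3.3.4 has no CORE-OM at follow-up for anyone, so it belongs there only if it is added for all women.

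Cross-refer to this from 3.3.4, 7.5 and 11.3. Report each withdrawn woman individually, with her reason and last available scores. The analysis set and any sensitivity summary can be left to the statistical analysis plan. Leave the clinical withdrawal criteria as they are.

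The cost is revised wording in the protocol, participant information sheet and consent form, a few extra mailings, and some contact with women who have left the group. All clients remain with the Perinatal Service for the duration of the research (section 7.6), so their care team can be asked. The change is best made before the group starts, since scores not collected cannot be recovered later.

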7.9 End of trial

The sponsor will notify the MHRA of the end of a clinical trial within 90 days of its completion. The completion date is scheduled for February 2021.

8 STATISTICS AND DATA ANALYSIS

This is a Case Series. No statistical review necessary as only frequencies and associations will be assessed – details of statistical input not required.

9 DATA MANAGEMENT

9.1 Data handling and record keeping

Participants are already patients of the GMMH Perinatal Community Mental Health Team service. Their personal details and clinical records are recorded on the trust electronic database PARIS.

A paragraph summary of each client's session will be uploaded to PARIS by the Chief investigator covering participant's attendance at the group, the headline theme of CBGT conducted during the session and a brief risk assessment.

Any electronic information sent via NHS.net email will either be uploaded to the client's PARIS notes if clinically relevant or recorded on the Chief investigator's secure GMMH 'Surface' trust laptop for the purpose of the research study. Once this is done the email will be deleted from the nhs.net email server.

Any physical paper information sent via post will either be scanned and uploaded to the client's PARIS notes if clinically relevant or scanned and recorded on the Chief investigator's secure GMMH 'Surface' trust laptop for the purpose of the research study. Once this is done the physical correspondence will be shredded.

Each CBGT session will be recorded via Microsoft Teams on the research lead's GMMH secure trust laptop. This information will not be moved or transferred from that computer. It will not be stored on any hard drive apart from the Chief investigator's secure trust laptop. It will not be stored on an external drive or cloud storage service.

Research information obtained during sessions will be recorded in a password protected document on the Chief Investigator's secure trust computer.

The research data and write up will be stored on the Chief Investigator's GMMH secure trust laptop. This is password encrypted, with password resets required on a 45 day basis. If the incorrect password is repeated the computer locks both the hardware and user's account.

This laptop will be kept in two locations. Locked securely at the Chief investigator's place of work (locked in a filing cabinet to which only the Chief investigator has access, the filing cabinet is in the consultant's locked office, to which only the Chief investigator and his secretary has access). Locked securely at the Chief investigator's home address in a filing cabinet to which only the Chief investigator has access.

Once the information is anonymised and the research write up commenced a backup copy of the research will be kept on a GMMH trust approved AES 256-BIT encrypted flash drive. This is required in case of a breakdown of the Chief investigator's trust laptop. This flash drive will be kept at the Chief investigator's home in a locked drawer to which only he has access.

9.2 Access to Data

The client's trust professional(s) will already have access to client records (via the GMMH trust electronic system - 'PARIS') for the purpose of CMHT perinatal treatment and care. The client's professional(s) will refer to these for the initial purpose of exclusion / exclusion criteria.

At the assessment interview access to client records (via the GMMH trust electronic system – 'PARIS') will be requested by the Chief investigator for the purpose of undertaking the clinical assessment and confirming inclusion / exclusion criteria. Clients will be asked for consent regarding this request.

Personal addresses and contact details will be viewed on PARIS to allow Participant Information Sheets (PIS) to be sent to clients; to contact clients for interviews; to write to thank clients for their participation; to send details of the findings to clients who elect to receive them. This information will not be viewed on PARIS unless required for these purposes. PIS and consent forms will be sent via email (www.nhs.net) or via post.

Only the Chief investigator ([name]) will have access to this data relating directly to the research study only. Clients will be asked for consent for this.

The co-facilitator ([name]) will be present during the CBGT sessions. Therefore he will be part of any CBT discussion and disclosure of information that occurs. However [name] will not have access to patient records on PARIS (and will not be expected to require this access). Furthermore [name] will not be involved in the write up of the research project, that is the responsibility of the Chief investigator. Anonymised data may be shared between [name] and [name] via secure, password protected email. This will be for the purpose of facilitating the group and planning each CBT session. No files containing identifying patient details will be transferred electronically between [name] and [name].

Anonymised findings may be discussed in the course of supervision between the Chief investigator ([name]), clinical supervisor ([name]) and university supervisor ([name]).

9.3 Archiving

Data relating to the research study will be kept in accordance with GMMH Standard Operating Procedure (RDSOP21 – Retention of Data, Off-site Archiving and Destroying of Documents). Electronic archiving will be undertaken for a retention period of 5 years from completion of study or submission of final report.

If a client contributes information clinically relevant to their perinatal care, this will be recorded on the GMMH electronic trust record 'PARIS'. The lead author will complete a paragraph summary of each client's session and upload this to PARIS. This will cover participant's attendance at the group, the headline theme of that CBGT session and a brief risk assessment. Once uploaded this information will remain on PARIS as part of the participant's clinical record.

10 ETHICAL AND REGULATORY CONSIDERATIONS

10.1 Research Ethics Committee (REC) review& reports

Prior to the start of the trial a favourable opinion will be sought from NHS REC and HRA for the trial protocol, consent letters and relevant documents.

10.2 Peer review

The protocol will be reviewed by an independent reviewer, who has the knowledge in the field and is familiar with the analysis described in the study.

10.3 Public and Patient Involvement

Mothers in the Greater Manchester Mental Health NHS Foundation Trust Perinatal Service have requested alternative treatments to medication. Feedback from an earlier service evaluation of a Cognitive Behavioural Therapy orientated Perinatal Group found mothers reported the group as beneficial for those who attended regularly. Mothers stated they would recommend the group to a friend.

A focus on difficulties specific to motherhood was highlighted as a particularly helpful aspect of such a Perinatal CBT group.

10.4 Regulatory Compliance

The trial will not commence until a Favourable REC opinion.

10.5 Protocol compliance

Prospective, planned deviations or waivers to the protocol are not allowed under the UK regulations on Clinical Trials and must not be used e.g. it is not acceptable to enrol a participant if they do not meet the eligibility criteria or restrictions specified in the trial protocol

Accidental protocol deviations can happen at any time. They must be adequately documented on the relevant forms and reported to the Sponsor immediately.

Deviations from the protocol which are found to frequently recur are not acceptable, will require immediate action and could potentially be classified as a serious breach.

